Secondary Objectives:	
1) To assess trough concentrations, accumulation and apparent terminal half-life of MPA, and the impact of subcutaneous injection site (abdomen, upper thigh, or upper arm) on these parameters, when Sayana® Press is injected every 4 months for 12 months of use;2) To evaluate the safety of Sayana® Press when injected every 4 months for 12 months of use;3) To evaluate the acceptability of Sayana® Press when injected every 4 months for 12 months of use.

Secondary Endpoints: Serum MPA concentrations on day 0 (baseline), months 2, 3, 4, 8, and 12 after treatment initiation (subset of 120 participants, only); serious adverse events and adverse events leading to product withdrawal; injection site reactions, bleeding patterns, blood pressure, and body weight; and responses to acceptability questions.

Exploratory Objective: To evaluate return to ovulation among a subset of study participants who received month 4 and month 8 injections and plan to use non-hormonal methods of contraception, or no contraception, for up to a maximum of 12 months from the last study injection.

Exploratory Endpoint: Return to ovulation, where ovulation is defined as a single elevated serum progesterone ($P \geq 4.7 \text{ ng/mL}$) or a confirmed pregnancy test.

General Design and Methodology:

This study will evaluate the effectiveness, pharmacokinetics (PK), safety, and acceptability of Sayana® Press when injected every 4 months (17-18 weeks) for 3 treatment cycles (12 months) of use. A total of 750 healthy, sexually active women aged 18 to 35 years with regular menstrual cycles and no DMPA use in the previous 12 months will be enrolled and followed for pregnancy. Among all enrolled, 710 will be randomized to receive injections in the abdomen or upper thigh in accordance with the PATH Sayana® injection instructions (Appendix 1), which are consistent with prescribing information, for the primary effectiveness analysis. An additional 40 women will be randomized to receive injections subcutaneously in the back of the upper arm to assess whether differences in PK may exist which could impact the grace period for reinjections for that injection site.

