The 710 women receiving injections in the abdomen or upper thigh will constitute the primary efficacy population. This study size is sufficient to ensure that the difference between the estimated Pearl Index (pregnancies per 100 woman-years of use) and the corresponding upper 95% confidence bound does not exceed 1.0, so long as the observed index is less than 0.75 and at least 80% of participants complete 12 months of follow-up. The PK cohort of 120 women (40 receiving injections in each the abdomen, upper thigh, and back of the upper arm) is sufficient to provide 85% power to detect 30% relative differences in PK parameters between injection sites, assuming the coefficient of variation is no more than 40% and using two-sided 0.05 significance tests.

Interim analysis:

An independent Data and Safety Monitoring Board (DSMB) will review interim data when 250 participants have completed 4 months of follow-up. This single, pre-planned interim analysis is intended to inform a decision whether to stop or modify the study (e.g., drop an injection site) if the estimated probability of pregnancy is greater than 2% in the first injection interval. Additional interim analyses may be requested by the DSMB based on periodic reviews of study indicators (pregnancy, adverse event, recruitment and continuation rates) if deemed necessary to protect participant safety or to make recommendations to modify the study.

TABLE OF CONTENTS

INVESTIGATOR SIGNATURE FORM	3
CLINICAL STUDY SYNOPSIS	4
LIST OF ABBREVIATIONS	13
1 BACKGROUND INFORMATION	14
1.1 Introduction	14
1.2 Name and Description of Product	15
1.3 Findings from Nonclinical and Clinical Studies	15
1.3.1 Nonclinical Studies	15
1.3.2 Clinical Studies	16
1.4 Known and Potential Risks and Benefits to Human Participants	19
1.4.1 Known and Potential Health Risks of the Study Drug	19
1.4.2 Benefits to Participants	21
1.5 Selection of Drugs and Dosages	21
1.6 Compliance Statement	21
1.7 Population to Be Studied	22
2 PURPOSE OF THE STUDY AND STUDY OBJECTIVES	22
2.1 Purpose of the Study	22
2.2 Study Objectives	22
2.2.1 Primary Objective	22
2.2.2 Secondary Objectives	22
2.2.3 Exploratory Objective	22
2.3 Study Endpoints	23
2.3.1 Primary Endpoint	23
2.3.2 Secondary Endpoint	23
2.3.3 Exploratory Endpoint	23
3 STUDY DESIGN	23
3.1 General Design and Study Schema	23
3.2 Justification for the Study Design	25
3.3 Efficacy Measure	25
3.4 Pharmacokinetic Measures	26
3.5 Safety Measures	26
3.6 Acceptability Measures	26

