1.3.2 Clinical Studies

1.3.2.1 Pharmacokinetics

The clinical pharmacology section of the Sayana® Press label was primarily informed by the study of Jain et al. which evaluated the PK profile of Depo-subQ Provera 104® and reported an average maximum serum concentration (C_{max}), 3-month trough (C_{3mo}), apparent terminal half-life ($t_{1/2}$), and area under the serum concentration-time curve (AUC) extrapolated to infinity of 1.56ng/mL, 0.40 ng/mL, 43 days, and 92.8 ng•day/mL, respectively [10]. Neither the manuscript nor the product label reports the site of injection used in the Jain study. Toh et al. evaluated the impact of injection site on PK of Depo-subQ Provera 104® among Asian women, and found a significantly lower C_{max} for injections in the abdomen than in the thigh (0.94 ng/mL versus 1.65 ng/mL). Mean $t_{1/2}$ and C_{3mo} were larger for the abdomen (104 days and 0.47 ng/mL, respectively) than the thigh (81 days and 0.41 ng/mL), but the differences were not statistically significant [19]. A PK/PD study comparing Sayana® Press to Depo-subQ Provera 104® in pre-filled glass syringe also failed to report the site of injection, but the average C_{max} for each device group (0.95 ng/mL and 0.79 ng/mL, respectively [17]) was consistent with the abdominal data in Toh et al. [19]. The mean MPA profile observed in a study of Depo-subQ Provera 104® injected in the upper arm was also more similar to the Toh et al. abdomen data [20], although the variability of $t_{1/2}$ and trough concentrations appeared higher with the upper arm injection site. Finally, the accumulation of MPA reported in an efficacy study of Depo-subQ Provera 104® [12] was consistent with a noticeably longer $t_{1/2}$ than reported by Jain et al. (Figure 1, inset). Overall, these data support the conclusion that, on average, the apparent terminal half-life of MPA may be longer than indicated by the Depo-subQ Provera 104® label, and that the PK of MPA may differ by injection site.

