Figure 1. Serum MPA concentrations (ng/mL) following injection of Depo-subQ Provera 104® in the thigh (black) or abdomen (purple; [19]), and the labelling study (blue; [10]). Shaded areas are +/- 1 SE of modeled means, assuming a constant 45% coefficient of variation. Inset includes predicted drug levels three months after a 2nd injection based on a half-life of 50 days (blue dot) or 90 days (black dot), and the mean trough concentration observed in an efficacy study following second injection (red dot; [12]).

Study	Injection site	N	Mean (SD) PK Parameter Estimates		
			C_{max} (ng/ml)	C_{3mo} (ng/ml)	$t_{1/2}$ (days)
Jain et al. [10]	Not specified	42	1.56 (0.67)	0.40 (0.15)	43.2 (20.8)
Toh et al. [19]	Thigh	12	1.65 (0.66)	0.41 (0.12)	80.9 (44.2)
Toh et al. [19]	Abdomen	12	0.94 (0.20)	0.47 (0.22)	103.7 (71.5)
Halpern et al. [20]	Upper arm	25	0.95 (0.31)	0.43 (0.35)	247.3 (534)
Sayana® Press [17]*	Not specified	60	0.88 (0.42)	Not specified	Not specified

[figure not shown]
* pooled across injection devices

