3.2 Justification for the Study Design

The study is designed to meet criteria for assessing the efficacy of hormonal contraceptive products specified in the European Medicines Agency Guideline on Clinical Investigation of Steroid Contraceptives in Women[31]. Specifically, at least 400 women completing one year of use and sufficient total months of use to obtain a 95% confidence interval for the Pearl Index (pregnancies per 100 WY of follow-up) with a half-width of no more than 1%. A study size of 710 women receiving injections in the abdomen or thigh is expected to achieve these criteria, while also allowing us to assess whether pregnancy risk may differ between these two injection sites.

The PK cohort will allow us to inform an appropriate grace period for re-injections based on estimated trough concentrations and apparent terminal half-life. Although the Product Leaflet for Sayana® Press specifies that injections are to be administered in the abdomen or thigh [29], back of the upper arm injection instructions are provided by PATH and the back of the upper arm is used by some providers ([32], Appendix 1). By randomizing an additional N=40 women to receive injections in the back of the upper arm we will be able to confirm findings from a previous non-comparative PK study which indicated MPA concentrations are more variable when drug is administered in this anatomical site [20], and inform the potential impact of any excess variability on efficacy.

To inform how much sooner women may expect to return to ovulation (and therefore, to fertility) when shifting from a 3-month to a 4-month dosing regimen, we will evaluate return to ovulation among a subset of study participants who received both month 4 and month 8 injections and plan to use a non-hormonal method of contraception, or no contraception, after study discontinuation, until resumption of ovulation or up to a maximum of 12 months from the last study injection, whichever comes first. We will also test for pregnancy, and measure levels of MPA and other synthetic steroids (e.g., levonorgestrel, etonogestrel and ethynodiol) to rule out concurrent use of other hormonal contraceptives that may suppress ovarian activity.

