3.4 Pharmacokinetic Measures

The PK of MPA will be evaluated among participants in the PK cohort based on estimated trough concentrations at month 4 ($C_{4\text{mo}}$), month 8 ($C_{8\text{mo}}$), and month 12 ($C_{12\text{mo}}$); apparent half-life ($t_{1/2}$); and accumulation of MPA over 3 cycles of use.

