10.1 Sample Size and Power Considerations

The sample size of 710 women receiving injections in the abdomen or thigh is expected to be sufficient to ensure that the difference between the estimated Pearl Index and the corresponding upper 95%

confidence bound does not exceed 1.0, so long as the observed index is less than 0.75 and at least 80% of participants complete 12 months of follow-up. In addition, a cohort of 120 women (40 per SC injection site) is sufficient to provide 85% power to detect 30% relative differences in PK parameters between injection sites, assuming the corresponding coefficient of variation is no more than 40% and using two-sided 0.05 significance tests.

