Treatment will begin in the first 5 days of menses. A single MPA serum sample will be collected from all participants at baseline. All participants will be scheduled to receive re-injections at month 4 (approximately 17 weeks after treatment initiation) and month 8 (approximately 35 weeks after treatment initiation) and complete their planned follow-up at month 12 (approximately 53 weeks after treatment initiation). There will be a plus 7-day grace period for re-injections, but women who are up to 28 days late may continue treatment if they have a negative urine pregnancy test. Urine pregnancy testing will be performed at month 4, at study exit, at month 8 if the participant is more than 7 days late for her visit, and at any time during the study if clinically indicated. Participants will be evaluated for injection site reactions and asked to provide information on adverse events, prohibited concomitant medications and other contraceptive use, vaginal bleeding, and method acceptability at months 4, 8 and 12. Information on adverse events and use of any prohibited concomitant medications will be recorded if reported by participants at month 2 and 3 PK visits and at any unscheduled visits.

III. General Analytic Considerations

A. Study Size and Power

The sample size of 710 women receiving injections in the abdomen or upper thigh is expected to be sufficient to ensure that the difference between the estimated Pearl Index (pregnancies per 100 woman-years of use) and the corresponding upper 95% confidence bound does not exceed 1.0, so long as the observed Pearl Index is less than 0.75 and at least 80% of participants complete 12 months of follow-up. (The study has a 90% chance of achieving this precision target if the true (unobserved) pregnancy rate is no more than 0.5 per 100 women-years). In

addition, a cohort of 120 women (40 receiving injections in each the abdomen, upper thigh, and back of the upper arm) is sufficient to provide 85% power to detect 30% relative differences in PK parameters between injection sites, assuming the coefficient of variation is no more than 40% and using two-sided 0.05 level significance tests.

B. Data Source

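### The 85% PK power is correct under its own 40% CV condition, but the protocol's table does not support that condition for upper-arm contrasts or for half-life

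*Protocol*

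**What the plan says.** Protocol 10.1 gives 40 women per injection site "85% power to detect 30% relative differences in PK parameters between injection sites, assuming the corresponding coefficient of variation is no more than 40" per cent, with two-sided 0.05 tests. The synopsis makes the same statement, "assuming the coefficient of variation is no more than 40% and using two-sided 0.05 significance tests", and so does SAP III.A, "no more than 40% and using two-sided 0.05 level significance tests". One CV ceiling serves trough and half-life alike, and all three pairs of sites. The 30% has no stated direction.

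The prior data are in the table in Protocol 1.3.2.1. The Figure 1 caption there models concentrations "assuming a constant 45% coefficient of variation". The accompanying text says that the variability of half-life "and trough concentrations appeared higher with the upper arm injection site", and Protocol 3.2 sets out to confirm the result of a non-comparative PK study that "MPA concentrations are more variable when drug is administered in this anatomical site". The synopsis gives the reason for adding 40 upper-arm women: to "assess whether differences in PK may exist which could impact the grace period for reinjections for that injection site".

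Protocol 3.4 evaluates PK "based on estimated trough concentrations at month 4", at months 8 and 12, and through half-life and accumulation. Protocol 10.7.2 compares sites by 95% intervals for geometric mean ratios of half-life and trough. SAP X.A compares the terminal phase by an overall test of intercepts and slopes from a mixed model, with pairwise tests only if that is significant at 0.05. It does not repeat the between-site ratio intervals.

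**The concern.** The power statement depends on a CV of at most 40%, and the same protocol tabulates CVs well above that for the upper arm and for half-life. Its text also expects the upper arm to be more variable. The contrasts that the arm group was added to inform are therefore the ones that the 85% fits least well.

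What is at stake is interpretation. Someone who takes 85% as the power of every contrast could treat a non-significant arm or half-life comparison as evidence that the sites are alike. The SAP makes this easier, because its between-site comparison is a gated significance test and the protocol's ratio intervals are not carried over.

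**Working it through.** **Method.** Two-sample comparison of log values. Log SD: s = sqrt(ln(1 + CV²)). Standard error of the log ratio: SE = sqrt((s1² + s2²)/40). Power is from the noncentral t with Welch degrees of freedom and noncentrality |ln ratio|/SE, two-sided 0.05. ln 1.30 = 0.262; ln 0.70 = -0.357.

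**Reproducing the 85%.** CV 40% gives s = sqrt(ln 1.16) = 0.385 and SE = 0.385 × sqrt(2/40) = 0.0861. Noncentrality is 0.262/0.0861 = 3.05 and power is 85.3%. A ratio of 1/1.30 = 0.77 gives the same. A ratio of 0.70 gives 98.3%. So the stated figure corresponds to 1.30 or 0.77, with 40 evaluable women per site and no allowance for losses.

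**CVs from the table in Protocol 1.3.2.1 (SD/mean).**

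| Source | N | 3-month trough | Half-life |
|---|---|---|---|
| Labelling study, site not specified | 42 | 0.15/0.40 = 37.5% | 20.8/43.2 = 48% |
| Thigh | 12 | 0.12/0.41 = 29% | 44.2/80.9 = 55% |
| Abdomen | 12 | 0.22/0.47 = 47% | 71.5/103.7 = 69% |
| Upper arm | 25 | 0.35/0.43 = 81% | 534/247.3 = 216% |

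At 37.5% in both groups, power is 89% for 1.30 and 99% for 0.70, so 40% is a fair general trough assumption. At the caption's 45% in both groups it is 77% and 96%.

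**Single trough, tabulated CVs.** Log SDs are 0.287 (thigh), 0.445 (abdomen) and 0.713 (arm).

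| Contrast | SE | Power, 1.30 | Power, 0.70 | 95% interval if observed ratio is 1.0 |
|---|---|---|---|---|
| Abdomen vs thigh | 0.0837 | 87% | 99% | 0.85 to 1.18 |
| Arm vs thigh | 0.1215 | 56% | 82% | 0.78 to 1.28 |
| Arm vs abdomen | 0.1329 | 49% | 75% | 0.77 to 1.30 |

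**Uncertainty in the arm CV.** A chi-square interval on the log variance (0.508, 24 df, lognormal assumption) runs from 24 × 0.508/39.4 = 0.310 to 24 × 0.508/12.4 = 0.983, a CV of roughly 60% to 130%. At 60%, power at 1.30 is 74% vs thigh and 63% vs abdomen; at 0.70 it is 94% and 88%. At 130%, it is 35% and 32% at 1.30, and 57% and 53% at 0.70.

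**Uncertainty in abdomen vs thigh.** The mean log variance is (0.287² + 0.445²)/2 = 0.140, a common CV of 39%. With Satterthwaite df of about 19, its 95% limits correspond to a common CV of about 29% to 59%, and to power at 1.30 from about 98% down to 56%.

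**Half-life.** Every tabulated CV exceeds 40%. The SAP derives half-life from model slopes over months 2 to 4, and the documents do not give the slope and within-woman variances, so the power of that analysis cannot be computed.

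**The case against.** The strongest reply is that the plan contains no error. The sentence is conditional, the condition is in plain view, and the calculation reproduces. That stands. A reader might infer a miscalculated power or a badly chosen CV; the documents support neither, since the largest sample with a trough SD (42 women) has a CV of 37.5%. What remains is scope: the condition is applied to contrasts for which the same document's data do not meet it.

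Second, 49% to 56% might be read as the trial's actual power for the arm. It is not. It comes from 3-month CVs in 12 to 25 women, whereas the trial's troughs are at months 4, 8 and 12. It also describes a single-time comparison, while the SAP tests mixed-model intercepts and slopes.

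Third, direction matters. If the grace-period question concerns low arm levels, 0.70 may be the relevant ratio; the arm contrasts then have 82% and 75%, and exceed 85% if the arm CV is near 60%. The plan states no direction, so this cannot be settled from the documents. The same caution applies to half-life: a rough comparison of individual half-lives at the labelling CV of 48% gives 72% for 1.30 but 93% for 0.70. The 40% condition fails for half-life, but it does not follow that power is below 85% under every definition of 30%.

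Fourth, nothing in the plan says that non-significance will be read as similarity, and Protocol 10.7.2 already plans ratio intervals. That limits the harm, but SAP X.A does not carry those intervals over.

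**Conclusion.** The concern holds as a minor correction to a secondary objective. The 85% is right for a ratio of 1.30 or 0.77, 40 evaluable women per site and a CV of at most 40%. The prior data are compatible with that condition for abdomen vs thigh trough (about 87%), but not for upper-arm contrasts or half-life. For a single arm trough, the indicative power at 1.30 is 56% vs thigh and 49% vs abdomen, or 74% and 63% if the arm CV is near 60%. At 0.70 it is 82% and 75%, or 94% and 88%. These figures assume lognormal values and that 3-month CVs carry over to the trial's troughs.

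Two stronger readings should be resisted. One is that 85% is assured for abdomen vs thigh: those CVs come from 12 women each, and the plausible range reaches down to 56%. The other is that the PK cohort is too small for its purpose: confirming greater variability at the arm is itself a stated aim, and the planned comparison of variance components is unaffected. The primary Pearl Index analysis is also unaffected.

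**What to change.** In Protocol 10.1, the synopsis and SAP III.A:

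1. State the 30% effect as a geometric mean ratio with its direction, noting that 85% corresponds to 1.30 or 0.77.
2. Keep the 85% as conditional on a CV of at most 40%. Add that prior data are compatible with this for abdomen vs thigh trough, but not for upper-arm contrasts or half-life.
3. Give the lower upper-arm trough power as an indicative range in both directions, with its source (3-month CVs, 12 to 25 women) and its limits. State no power for half-life.

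In SAP X.A:

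4. Carry over the between-site 95% intervals for geometric mean ratios of half-life and trough from Protocol 10.7.2, and say that a non-significant arm or half-life comparison will not be read as similarity.

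The cost is a less favourable stated figure and the ethics approval that Protocol 12.1 and 13.3 require for a protocol change. No participants are added, and the design and primary analysis stay as they are.

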10.2 Analysis Populations and Analysis Sets

In the below definitions, an Analysis Population refers to a particular set of participants and an Analysis Set defines the time contributed to analyses by participants in a given Population. Additional censoring rules for analyses based on these sets are described in relevant sections of the SAP.

10.2.1 Treated Population and Analysis Set

The Treated Population consists of all screened participants who are enrolled and receive a dose of study drug. For the primary efficacy analysis, the corresponding Treated Analysis Set includes all follow up time contributed by each participant in the Treated Population until their EDF, the end of their treatment period, or the date of their last negative urine pregnancy test (for participants who do not become pregnant), whichever is earlier. Comparative efficacy analyses based on SC injection site will be performed according to intention-to-treat principles, ignoring any randomization or allocation errors.

10.2.2 Pharmacokinetics Population and Analysis Set

The Pharmacokinetics Population is a subset of the Treated Population, excluding participants who did not contribute blood specimens for PK assessments or who had a baseline serum MPA concentration exceeding 0.05 ng/mL. The corresponding Pharmacokinetics Analysis Set will censor data collected after a participant receives an injection in an anatomical site which differs from the site used at enrollment and will exclude any MPA specimens collected during a time when a participant reports use of a concomitant medication that may impact the PK of MPA. PK analyses based on this analysis populationconmed will be performed according to the SC site of injection at enrollment, even if received in error.

10.2.3 Extended Follow-up Population

The Extended Follow-up Population is a subset of the Treated Population, including participants who meet criteria for the extended follow-up subset and consent to remain in follow-up past their month 12 visit in order to provide information on return to ovulation.

10.3 Data Handling Conventions

Estimated dates of fertilization will be adjudicated following FHI 360 SOPs based on ultrasound reports, LMP, or best clinical judgment (if ultrasound results are not available). It is anticipated that some event dates required for safety analyses may be incomplete. For example, participants may not recall the exact day of onset for a self-reported AE. Decision rules for how and when to impute such incomplete date fields will be developed by the medical monitor when reviewing study data and be documented in the study report. Other missing outcome or predictor variables will be ignored unless patterns are identified

which suggest the potential for biased assessments of efficacy, safety, PK or acceptability. In that event, rules for imputing data will be clearly described and justified in the study report.

